4.3 Risks and Benefits

- The benefits of using neuromuscular blockade monitoring devices:
Early detection of optimal time for tracheal intubation; optimal management of intraoperative depth of neuromuscular block to facilitate surgical procedures;

determination of appropriate time and dose of sugammadex reversal; and detection of residual neuromuscular blockade

- The risks of using neuromuscular blockade monitoring devices:
Slight discomfort when electrical stimulation is administered in awake volunteers; however, our patients will be anesthetized, rendering this risk as extremely minor.

5 Study Objectives

Primary Objective

To compare the time to onset of blockade, level of blockade prior to reversal, and the rate of recovery between flexor hallucis brevis and adductor pollicis muscles following sugammadex administration.

Secondary Objective

Determine the incidence of postoperative residual weakness at the time of extubation at a center that predominately utilizes quantitative monitoring (defined as TOFR <0.90) and sugammadex.

6 Study Design

6.1 General Description

[figure not shown]
This pilot unblinded, single center, prospective, randomized, observational study will involve 130 patients undergoing surgical procedure that requires administration of neuromuscular blocking agents intraoperatively.

6.2 Number of Subjects

One hundred twenty

6.3 Duration of Participation

2-5 hours, depending on duration of surgery

6.4 Primary Study Endpoints

The primary endpoint of the study will be time of onset of blockade and the rate of recovery following sugammadex administration as recorded simultaneously from the hand (adductor pollicis) and foot (flexor hallucis brevis) muscles.

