9.2 Visit 2 (Randomization and Treatment – day of surgery)

- Elective surgical procedure as per standard of care
- Anesthetic management will include rocuronium, sevoflurane, and sugammadex at the discretion of the attending anesthesiologist as per standard of care practice.
- Prior to induction of anesthesia, Tetragraph electrodes will be placed over the ulnar nerve and the thumb to measure the response of adductor pollicis, and over the posterior tibial nerve and the great toe to measure the response of the flexor hallucis brevis.
- Following induction of anesthesia but prior to NMBA administration, baseline values will be recorded at both muscle groups after instrument calibration.
- Near the conclusion of the operation but prior to reversal of NMBA, another set of measurements will be taken at both muscle groups.
- Intraoperatively, measurements will be taken every minute until the sugammadex administration, as per usual clinical routine.
- After sugammadex administration, measurements will be taken every 20 seconds until the patient's trachea is extubated.
- Anesthesia providers will be guided on the intraoperative management of neuromuscular block based on the responses recorded from the adductor pollicis muscle, as per usual clinical routine.
- Each neurostimulation with the TetraGraph will be conducted simultaneously by a single study team member.
- Following measurements obtained with both devices at these specified time intervals and assuming TOF ratio is >0.9 , the devices will be disconnected and the patient will proceed along the standard recovery pathway.

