10.2 Statistical Methods

Descriptive Statistics

Analysis of agreement between the muscle groups will be compared between the two monitoring sites using the Wilcoxon signed rank test. The limits of agreement are defined as $\text{bias} \pm 2 \text{ SD}$, where SD denotes the standard deviations of the differences. Limits of agreement are interpreted as the reference range within which 95% of the differences will lie. The bias and the limits of agreements surrounding the bias ($\pm 2 \text{ SD}$) will be calculated with 95% confidence intervals. Statistical significance will be defined as a p-value <0.05 .

Handling of Missing Data

This is a prospective pilot study and therefore we do not anticipate any missing data. In the event of any unexpected missing data, no attempt to impute this missing data will be made;

missing data will simply be treated as missing in the statistical analysis, and replacement participants will be enrolled to achieve the target accrual of n=100 participants.

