18.3 Monitoring data

Study ID				
Date of Surgery (dd / mm / yyyy):				
Initials:		Dominant side:	L / R	Age (yrs):
Wrist circumference (right):		Wrist circumference (left):		
Ankle circumference (right):		Ankle circumference (left):		
Weight (kg):		Height (cm):		BMI:

TetraGraph (TG)

Arm tested: dominant / non-dominant

	Thumb	Toe	TOFR #3 (if needed)
Calibrated baseline TOFR and supramax current			
Time to TOFC=0			
pre-SGX			
+20 sec			
+40 sec			
+60 sec			
+120 sec			
+140 sec			
+180 sec			
+200 sec			
+220 sec			
+240 sec			

+260 sec			
TOFC or TOFR +280 sec			
TOFC or TOFR +300 sec			
TOFC or TOFR at extubation			
Time to recovery following SGX (TOFR ≥ 0.9) (two consecutive measurements)			

19 List of In-Text Figures

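### Rate of recovery is a primary endpoint with no definition, and no stated analysis separates it from the depth of block at sugammadex

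*Combined protocol and SAP*

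**What the plan says.** Section 5 sets three comparisons as the primary objective: onset, and "level of blockade prior to reversal, and the rate of recovery between flexor hallucis brevis and adductor pollicis muscles". Section 6.4 names as primary endpoint "time of onset of blockade and the rate of recovery following sugammadex administration", recorded at hand and foot together. Neither section defines the rate, and section 10 does not either.

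The data form in 18.3 has thumb and toe columns for a pre-sugammadex value, timed readings afterwards and a value at extubation. Its only derived recovery quantity is the final row, "Time to recovery following SGX (TOFR ≥ 0.9) (two consecutive measurements").

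Section 9.2 fixes how the data arise. On depth: "prior to reversal of NMBA, another set of measurements will be taken at both muscle groups". On recovery: "After sugammadex administration, measurements will be taken every 20 seconds until the patient's trachea is extubated". On management: "Anesthesia providers will be guided on the intraoperative management of neuromuscular block based on the responses recorded from the adductor pollicis muscle". Section 8.1 adds that the device stores the whole intraoperative recording for later download and analysis.

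Section 10.2 says that agreement between the muscle groups will be "compared between the two monitoring sites using the Wilcoxon signed rank test", with limits of agreement at bias ± 2 SD. It does not name the recovery variable to be tested, and it contains no adjustment, matching or stratification for depth before reversal.

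**The concern.** Time to a fixed threshold has two ingredients: how far the muscle still has to go, and how fast it goes. If the two sites stand at different depths when sugammadex is given, their times to TOFR 0.9 differ even when they recover at the same speed.

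The plan itself allows for unequal depth, because it makes depth before reversal part of the primary objective. It also steers block by the thumb, so nothing holds the toe at a comparable level. Pairing within patient does not help, because the depth gap is itself a within-patient difference.

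At stake is the meaning of a primary result. Section 4.1 gives the aim as learning how the two muscles differ in sensitivity to the blocking drug and to the reversal drug. Depth before reversal speaks to the first, while unadjusted time to 0.9 mixes both. A difference in response to the blocker could be read as a difference in response to sugammadex, or could hide one. A site already at 0.9 before sugammadex tells us nothing about recovery after it, and the plan has no rule for such a patient.

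**Working it through.** **1. The plan's own figure.** Inputs from 10.1: difference 0.5 min, SD 1.5 min, significance level 0.05, power 90%, paired t test. Two-sided testing is my assumption, and 1.5 min is taken as the SD of the paired differences.

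- Normal approximation: n = (SD × (z₀.₉₇₅ + z₀.₉₀) / difference)² = (1.5 × (1.960 + 1.282) / 0.5)² = 94.6, so 95.
- Exact noncentral t: n = 97, power 90.1%.

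The stated 97 reproduces. Section 10.1 does not say whether the 0.5 min is a difference in onset or in recovery. Its rationale refers to rapid sequence induction and intubation, which points to onset.

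**2. What time to 0.9 measures.** Let a site start at TOFR s and rise linearly at r per minute. Then time to 0.9 = (0.9 − s) / r. If r is the same at both sites, the thumb-minus-toe difference is (s_toe − s_thumb) / r, which is not zero unless the starting levels match.

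The reverse also happens. A thumb that starts at 0 and takes 2 min has a rate of 0.9 / 2 = 0.45 per min. A toe that starts at 0.2 and also takes 2 min has a rate of (0.9 − 0.2) / 2 = 0.35 per min. The times are equal and the rates are not.

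**3. Size, for illustration.** The documents give neither a depth gap nor a recovery time, so both are assumed. With T the time from 0 to 0.9, rate = 0.9 / T and shift = gap / rate.

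| T (min) | Rate (per min) | Shift, gap 0.2 (min) | Shift, gap 0.3 (min) |
|---|---|---|---|
| 1.5 | 0.60 | 0.33 | 0.50 |
| 2 | 0.45 | 0.44 | 0.67 |
| 3 | 0.30 | 0.67 | 1.00 |

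This needs a measurable TOFR at both sites before sugammadex. It does not describe patients in deeper block, where only a count (TOFC) is available.

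**4. What a test would make of such a shift.** Suppose the true rates are equal and depth alone moves the mean paired difference by b minutes. I borrow the SD of 1.5 min from 10.1, although it may not belong to recovery, and use a two-sided paired t test at 0.05. The plan names the Wilcoxon test, so these figures are approximate for it.

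| b (min) | p < 0.05, n = 97 | p < 0.05, n = 130 |
|---|---|---|
| 0.1 | 10% | 12% |
| 0.2 | 26% | 33% |
| 0.3 | 50% | 62% |
| 0.4 | 74% | 86% |
| 0.5 | 90% | 97% |

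Here b is an average shift in one direction. Gaps that vary in sign between patients would partly cancel in the mean.

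**5. Resolution of the serial readings.** Readings come every 20 s, or 0.33 min. Over one interval TOFR rises by 0.60 × 0.33 = 0.20 when T is 1.5 min, and by 0.30 × 0.33 = 0.10 when T is 3 min. A rate can be taken from these readings, but only coarsely when recovery is fast.

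**The case against.** The best defence is that the plan already looks at depth. It is a named comparison in section 5 and is recorded at both sites, so a reader of the results would see any gap beside the recovery times. Moreover, both muscles in one patient receive the same drug. Unequal depth is then arguably part of the site difference under study, and time from sugammadex to adequate recovery is a legitimate and clinically useful unadjusted comparison.

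Much of this stands, and it is a reason to keep that comparison. It does not justify calling the result a rate. Two separate group comparisons, one of depth and one of time, also do not show how much of the second is due to the first. If a rate is derived later without a definition, its start point and method will be chosen after the data are seen. Section 6.1 calls the study a pilot, but 10.1 sizes it at 90% power for a difference between sites.

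Three stronger readings are tempting and are not supported:

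- *The plan captures no recovery data except time to 0.9.* It also collects depth before reversal, serial readings and a value at extubation at both sites. The gap lies in definition and analysis.
- *The plan will test time to 0.9 and report it as a rate.* Section 10.2 names no recovery variable. Time to 0.9 is simply the only derived one on the form.
- *A modest depth gap would produce or hide the study's target difference.* No depth gap is given, and the 0.5 min target is not tied to recovery.

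**Conclusion.** The point holds as a gap in endpoint definition and analysis. Rate of recovery is primary and undefined, the only derived recovery variable mixes speed with starting depth, and no stated analysis pulls the two apart although the data to do so are collected. A thumb-toe difference in time to TOFR ≥0.9 cannot, on the plan as written, be attributed to rate.

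The size is unknown. The 0.33 to 0.67 min for a 0.2 gap rests on assumed equal, linear recovery over 1.5 to 3 min. The rejection rates rest further on an SD of 1.5 min for paired differences in recovery time. Both show sensitivity and do not predict a result. The change should be made before analysis, because it concerns the primary endpoint and costs little.

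**What to change.** In 5 and 6.4, call the endpoint the time from sugammadex to TOFR ≥0.9, and keep its unadjusted paired comparison. In 10.2, name that variable and add two analyses:

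- **(a) Depth-accounted comparison.** Analyse the paired difference in time to 0.9 with the paired difference in depth before sugammadex as covariate. The site effect is then read at equal depth. Put TOFC and TOFR on one ordered scale. Alternatively, restrict to patients with the same TOFC, or closely matched TOFR, at both sites. A broad class such as any TOFR below 0.9 will not do: a thumb at 0.4 and a toe at 0.7 would count as matched with a gap of 0.3.
- **(b) Supportive interval comparison.** Compare the time each site takes to rise between two TOFR levels, fixed in advance and the same at both sites. Take it from the downloaded 20-second recordings, because the form in 18.3, as it reads in the available text, has no rows at +80, +100 or +160 sec. Starting from each site's own first measurable TOFR would bring the unequal start back in.

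Rest any conclusion on rate on (a) and (b). State the handling rules:

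- Report patients with a site already at ≥0.9 before sugammadex, and leave them out of the rate comparison.
- Treat a site not at 0.9 by extubation as censored.
- Report how many sites recover too fast between readings to give an interval.

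State in 10.1 whether the 0.5 min refers to onset or recovery. The cost is wording in 5, 6.4, 10.1 and 10.2 and two analyses of data already collected. The depth-matched and interval analyses will use fewer patients and be less precise, and the covariate form assumes a shape for the relation between depth and time.

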6.5 Secondary Study Endpoints

The secondary endpoint is the incidence of postoperative residual weakness at the time of extubation at a center that predominately utilizes quantitative monitoring (defined as TOFR <0.90) and sugammadex.

6.6 Identification of Source Data

The study data points will be recorded on the developed Case Report Forms (CRFs) by the study team members. In addition to the data collected intraoperatively ([Table 18.3](#)), several intraoperative characteristics will also be extracted from the medical record ([Table 18.2](#)). These will include type and total dose of NMBA used, time and dose of last NMBA administration, time and dose of specific reversal agent administration, time of tracheal extubation, and TOF ratio at the time of extubation (if available).

7 Subject Selection Enrollment and Withdrawal

7.1 Inclusion Criteria

- Age > or = 18 years old
- Patients willing to participate and provide an informed consent
- Patients undergoing an elective surgical procedure that requires use of non-depolarizing NMBA agents administered intraoperatively.
- Patients with planned administration of sugammadex as a neuromuscular blocking reversal agent.

7.2 Exclusion Criteria

- Patients with disorders, such as stroke, carpal tunnel syndrome, broken wrist with nerve damage, Dupuytren contracture, or any similar wrist injury.
- Patients with systemic neuromuscular diseases such as myasthenia gravis
- Patients with significant organ dysfunction that can significantly affect pharmacokinetics of neuromuscular blocking and reversal agents, i.e., severe renal impairment or end-stage liver disease.
- Patients having surgery that would involve prepping the arm or leg into the sterile field

7.3 Subject Recruitment, Enrollment and Screening

On a daily basis, there are over 20 elective surgical cases performed at Mayo Clinic in Florida and thus no difficulties in accrual are anticipated based on historical volumes. We will target at least 10 participants per week to complete this study. The initial accrual period will last at least 3 months followed by interim analysis and additional time for accrual will be determined to meet the target. Patients will be provided with a Research Participant Consent and Privacy Authorization Form describing the study devices, protocol, inclusion and exclusion criteria, as well as risks and benefits of participation.

7.4 Early Withdrawal of Subjects

7.4.1 When and How to Withdraw Subjects

Patients are free to withdraw at any time and for whatever reason. If patient withdraws consent prior to arrival to operating room, the study data will not be collected. If patient withdraws consent after study data was already completed, the participant will need to provide instructions to the study team to remove his/her data from the data set. Pre-specified reasons for discontinuing include, but are not limited to, the following:

- Patient Request: Patient decided that he/she did not want to continue (for any reason)

- Adverse Event: Patient experienced a related or unrelated event that would interfere with the study objectives/evaluation
- Inclusion/Exclusion Discrepancy/Violation: Patient should not have been enrolled
- Other: Any other reason

7.4.2 Data Collection and Follow-up for Withdrawn Subjects

If a Participant withdraws from the study, no additional attempts will be made to contact the Participant.

8 Study Device

8.1 Description

TetraGraph device is a FDA approved neuromuscular transmission monitor capable of measuring the depth of neuromuscular block in anesthetized patients who received neuromuscular blocking agents. TetraGraph uses EMG to measure the muscle action potentials that are generated in response to electrical neurostimulation via skin (ECG) electrodes. TetraGraph data is recorded on the monitor's built-in SD card, and all intraoperative data will be recorded and later downloaded for purposes of analysis. The recorded data do not contain PHI, only the date/time of recording, and any additional intraoperative interventions, such as the time of NMBA dose administration, time of antidote administration, time of extubation, etc. These events are flagged in the monitor's integrated SD card recordings.

8.2 Method for Assigning Subjects to Treatment Groups

This is an open-label pilot investigation and all study participants are assigned to both standard of care and investigational device use in the operating room. The randomization involves the use of dominant vs non-dominant arm. The placement of the lead on the great toe will correspond with the randomization assignment (if patient's dominant hand is right, and then the right great toe will be used).

The randomization will be performed utilizing REDCap and assigned anesthesia clinical care team will be informed of patients' assigned to guide them with the selection of the assigned treatment option.

8.3 Masking/Blinding of Study

This is an open-label investigation. Masking and blinding procedures are not applicable.

9 Study Procedures

9.1 Visit 1 (Screening and Enrollment up to the day of surgery)

- Review of medical record
- Informed Consent - Patients will be identified during their preoperative appointment and introduced to a study; they will be provided with a copy of the consent document and information about the study. The consenting will take place after additional discussion on the day of surgery.

9.2 Visit 2 (Randomization and Treatment – day of surgery)

- Elective surgical procedure as per standard of care
- Anesthetic management will include rocuronium, sevoflurane, and sugammadex at the discretion of the attending anesthesiologist as per standard of care practice.
- Prior to induction of anesthesia, Tetragraph electrodes will be placed over the ulnar nerve and the thumb to measure the response of adductor pollicis, and over the posterior tibial nerve and the great toe to measure the response of the flexor hallucis brevis.
- Following induction of anesthesia but prior to NMBA administration, baseline values will be recorded at both muscle groups after instrument calibration.
- Near the conclusion of the operation but prior to reversal of NMBA, another set of measurements will be taken at both muscle groups.
- Intraoperatively, measurements will be taken every minute until the sugammadex administration, as per usual clinical routine.
- After sugammadex administration, measurements will be taken every 20 seconds until the patient's trachea is extubated.
- Anesthesia providers will be guided on the intraoperative management of neuromuscular block based on the responses recorded from the adductor pollicis muscle, as per usual clinical routine.
- Each neurostimulation with the TetraGraph will be conducted simultaneously by a single study team member.
- Following measurements obtained with both devices at these specified time intervals and assuming TOF ratio is >0.9 , the devices will be disconnected and the patient will proceed along the standard recovery pathway.

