Overall Study Duration	12 months
Subject Participation Duration	2 to 5 hours
Single or Multi-Site	Single site
Objectives	The primary aim of this study is to assess the onset of neuromuscular blockade and recovery profiles of aminosteroidal NMBAs after sugammadex at the flexor hallucis brevis and adductor pollicis muscles
Number of Subjects	130
Diagnosis and Main Inclusion Criteria	Patients undergoing elective surgery and requiring administration of aminosteroidal NMBAs (rocuronium, vecuronium) intraoperatively
Study Device	TetraGraph
Duration of Administration	Single stimulation of flexor hallucis brevis and adductor pollicis muscles repeated at specific intervals as outlined in the Study Procedures (Section 9.2)

4 Introduction

This document is a protocol for a human research study. This study will be carried out in accordance with the applicable United States government regulations and Mayo Clinic research policies and procedures.

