4.1 Abstract

Residual neuromuscular blockade is a common occurrence in the post-anesthesia care unit (PACU) when neuromuscular blocking agents (NMBAs) have been used in the operating room. The only method of reliably detecting residual neuromuscular blockade is through the use of quantitative neuromuscular monitors. Unfortunately, several barriers exist that have prevented the widespread use of these devices. For instance, there is a paucity of quantitative neuromuscular monitors commercially available. Also, two modalities of quantitative monitoring, kinemyography and acceleromyography, rely on movement of the muscles of interest, a characteristic frequently compromised during patient positioning for surgical procedures in which the patient's arms are secured under surgical drapes (laparoscopic, bariatric, robotic, spine, and neurosurgical procedures) or in uncooperative awake patients in the PACU or intensive care unit (ICU). The aim of this investigation is to determine the different muscle sensitivities to NMBA and reversal agents by comparing responses at two different monitoring sites as measured with a new quantitative monitor. The TetraGraph (Senzime AB, Uppsala, Sweden) is a standalone electromyography (EMG)-based quantitative monitor that recently received Conformité Européene (CE) and US Food and Drug Administration (FDA) approvals. EMG measures electrical activity within the muscle following peripheral nerve stimulation, and is unaffected by involuntary patient motion or by restricted muscle movements from surgical positioning. We plan to compare measurements obtained with two Tetraphraph devices, one monitoring the adductor pollicis (thumb) muscle and the other monitoring the flexor hallucis brevis (great toe) muscle, during onset, maintenance, and recovery of neuromuscular blockade. This will include monitoring every 20 sec for onset of blockade (defined as Train-of-four count, TOFC =0) following rocuronium administration, during maintenance of neuromuscular block as required by surgical conditions, and following reversal administration until adequate recovery is documented (train-of-four ratio, TOFR > 0.9).

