Utilizing recommendations from the Good Clinical Research Practice (GCRP) Guidelines for monitoring of neuromuscular function (Fuchs-Buder et al. 2007), we will investigate the performance of the TetraGraph at two muscle groups: adductor pollicis and flexor hallucis brevis. Specifically, the time points of interest will include the onset of blockade (Train-of-four count =0), maintenance of neuromuscular block as clinically indicated by surgical needs, and recovery from rocuronium blockade with sugammadex, and every 20 seconds following reversal administration until tracheal extubation (as determined by the SOC practice).

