10.1 Sample Size Determination

Based on paired t test, 97 patients will provide 90% power to detect a difference of 0.5 min or larger between hands and feet at 0.05 significance level. A common standard deviation of 1.5 min for hands and feet is assumed based on previous work comparing flexor hallucis brevis and adductor pollicis muscles. However, we will enroll 130 patients to take into account patient loss or missing data. We want to determine a shorter time difference between hand and foot in order to make it applicable in all clinical settings, including rapid sequence induction and intubation.

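### Section 9.2 omits the 20 s onset reading interval set in Section 4.1; taken literally it has onset read once a minute, coarser than the 0.5 min hand-foot difference the study is sized for

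*Combined protocol and SAP*

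**What the plan says.** Section 6.4 makes the primary endpoint "time of onset of blockade and the rate of recovery following sugammadex administration", recorded at hand and foot together. Three places bear on how often onset is read.

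- Section 4.1 (Abstract): "This will include monitoring every 20 sec for onset of blockade", with onset defined as TOFC = 0. It lists maintenance as a separate phase, "during maintenance of neuromuscular block as required by surgical conditions".
- Section 4.2 (Background): "the time points of interest will include the onset of blockade (Train-of-four count =0), maintenance of neuromuscular block". It attaches 20 s only to the period after reversal.
- Section 9.2 (procedures on the day of surgery): a baseline before the blocking agent, a set before reversal, 20 s readings after sugammadex, and for the time before sugammadex "Intraoperatively, measurements will be taken every minute until the sugammadex administration, as per usual clinical routine". It has no onset step.

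The Study Summary (Section 3) defers to 9.2 for timing: stimulation is "repeated at specific intervals as outlined in the Study Procedures (Section 9.2"). Section 9.2 also states "Each neurostimulation with the TetraGraph will be conducted simultaneously by a single study team member". The form in 18.3 has a row for time to TOFC = 0 but gives no reading interval. Section 10.1 sizes the study: "97 patients will provide 90% power to detect a difference of 0.5 min or larger between hands and feet".

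**The concern.** Staff working from 9.2 would find no 20 s reading before sugammadex. Two readings of the section are possible. If its every-minute sentence covers maintenance only, the procedures give no interval for a component of the primary endpoint. If the sentence is literal, it conflicts with 4.1.

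On the literal reading the grid is twice as wide as the target difference (60 s against 30 s). With both sites read at the same moments, an onset difference can only be recorded as 0, 1, 2 and so on minutes in either direction. At stake are the resolution of each patient's difference, the number of zero differences entering the planned Wilcoxon signed rank test, the width of the limits of agreement, and a little power. The device download described in 8.1 cannot supply readings that were never taken.

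**Working it through.** **Inputs.** Target difference 0.5 min, SD 1.5 min, alpha 0.05, paired t test, n = 97, enrolment 130 (10.1). Reading intervals 20 s (4.1) and 60 s (9.2, literal). Limits of agreement at bias ± 2 SD and the signed rank test (10.2). Assumed, because the documents do not say: a two-sided test, and 1.5 min as the SD of the paired differences.

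**1. The plan's own figure.** The noncentrality is √97 × 0.5/1.5 = 3.28. The noncentral t gives power 0.901, and 97 is the smallest n reaching 90%. A one-sided test would need 79. So 97 is reproduced when the test is two-sided and 1.5 min is the SD of the differences. If 1.5 min is instead the SD at each site, this corresponds to a hand-foot correlation of 0.5.

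**2. What the grid adds.** Onset is recorded at the first reading with TOFC = 0, so each site is rounded up to a common grid of width g. Each rounding error has variance g²/12, so the difference gains g²/6.

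- 20 s: (1/3)²/6 = 0.0185 min², an error SD of 8.2 s. SD of differences √(2.25 + 0.0185) = 1.506 min.
- 60 s: 1/6 = 0.1667 min², an error SD of 24.5 s. SD of differences √(2.25 + 0.1667) = 1.555 min.

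**3. One patient.** A true difference of exactly 30 s is recorded as 0 or 60 s with equal chance on the 60 s grid, and as 20 or 40 s with equal chance on the 20 s grid. The error in a patient's difference is triangular on ±g. It exceeds 30 s with probability (1 − 30/60)² = 0.25 on the 60 s grid and never on the 20 s grid.

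**4. The group.**

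| | 20 s | 60 s |
|---|---|---|
| Limits of agreement (± 2 SD) | ±3.01 min | ±3.11 min |
| Paired-t power, n = 97 | 89.9% | 88.0% |
| N for 90% power | 98 | 104 |
| Paired-t power, n = 130 | 96% | 95% |
| Signed rank power, n = 97 (20,000 simulated trials, zeros dropped) | 88.8% | 87.1% |
| Type I error, signed rank | 4.9% | 4.9% |
| Mean recorded difference (2,000,000 simulated pairs) | 0.50 min | 0.50 min |
| Share of zero differences | 8.4% | 24.4% |

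The zero shares are about 8 and 24 of 97 patients. With a per-site SD of 1.5 min and correlations from 0 to 0.8, they run from 6 to 12 patients at 20 s and from 17 to 33 at 60 s. A further simulation with skewed onset times (assumed means of 3 and 5 min, correlation 0.5) gave power of 88 to 89% against 86 to 87%, and zeros in 9 to 10% against 26 to 28%.

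**5. If 1.5 min already contains reading error.** Section 10.1 takes the SD from earlier work and does not say how often onset was read there.

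| 1.5 min contains | SD 20 s / 60 s | Power at 97, 20 s / 60 s | N for 90%, 20 s / 60 s |
|---|---|---|---|
| no reading error | 1.506 / 1.555 | 89.9% / 88.0% | 98 / 104 |
| 20 s error | 1.500 / 1.549 | 90.1% / 88.3% | 97 / 103 |
| 60 s error | 1.450 / 1.500 | 92.0% / 90.1% | 91 / 97 |

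The gap between the grids stays at 1.8 to 1.9 points. In the last row the planned 90% is kept even on the 60 s grid.

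**The case against.** The strongest reply is that the two sections can be harmonised. Section 4.1 is specific to onset. The 9.2 sentence is general and tied to routine practice, so it can be taken as maintenance only. On that reading the defect is one sentence not copied into 9.2, and the figures above do not arise. This is a fair reading and may be what was meant. It still leaves the procedures without an interval for a primary endpoint component, in the section the summary points to.

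Second, a grid coarser than the target mean does not prevent its detection when the SD is 1.5 min. That stands. The mean is unbiased, the power loss is about 2 points, and at the n = 100 accrual target in 10.2 paired-t power is 89.0% against 90.8%. Uncertainty about the SD matters far more. If 1.5 min is the per-site SD, power at n = 97 (20 s against 60 s) is about 63% against 62% at correlation 0, and 99.9% against 99.7% at 0.8.

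Third, 10.1 does not name the endpoint behind 0.5 min. Its reference to rapid sequence induction points to onset, but that is an inference. Whole-minute differences also assume that the two devices run on one common grid, which 9.2 supports but does not guarantee.

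These points limit the weight of the concern. They do not remove the gap in 9.2.

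**Conclusion.** The concern holds, at modest size. Section 9.2 either omits the onset interval or contradicts 4.1, and neither 4.2 nor the form in 18.3 settles which. That rests on the text alone.

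The numerical cost applies only if 9.2 is followed literally. It also assumes simultaneous readings on a common grid and 1.5 min as the SD of the differences. It is a loss of per-patient resolution, roughly three times as many zero differences, limits of agreement about 0.1 min wider on each side, and just under 2 points of power at n = 97. The planned enrolment of 130 absorbs the power loss. No bias or inflation of type I error is expected. It should be fixed because it concerns a primary endpoint component and the missing readings could not be recovered.

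**What to change.** Reconcile 9.2 with 4.1. State in 9.2 that study readings at both sites are taken every 20 s from administration of the blocking agent until TOFC = 0 has been recorded at both. The interval is the one 4.1 already gives. The end of the 20 s phase is not spelled out there, but it follows from the endpoint definition. Label the every-minute sentence as the maintenance phase and leave it otherwise unchanged. The sentence on which site guides management of the block stays as written.

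As housekeeping, confirm that endpoint times are derived from the device download described in 8.1. Also check the rows of the 18.3 form against the 20 s schedule: +80, +100 and +160 s are absent from the extracted text, which may be an artefact of the PDF.

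The cost is one or two sentences. Readings every 20 s at both sites are already planned after sugammadex, so no new equipment or staff should be needed, though the documents do not discuss staffing at induction.
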